3.5 Design of Part B Expansion Cohorts

Once the MTD has been defined, preliminary activity will be further evaluated in the expansion part of the study. If clinically indicated, separate cohort(s) may be open for enrollment to evaluate a different schedule of PCLX-001 (for example a break within cycles), based on safety, PK and preliminary activity data and integrated PK/efficacy and PK/safety modelling from the dose escalation. The RP2D will be defined by the sponsor in conjunction with the investigators after reviewing the data from all parts and stages of the study, including available PK data and intensity of adverse events (AEs), and efficacy parameters, including overall response rate (ORR). The RP2D may be the MTD but not necessarily as not only safety data will be taken into account prior to its determination.

Two expansion cohorts will be opened to determine the preliminary clinical activity of PCLX-001. Part B dose expansion Cohort A will occur once the MTD and the RP2D are determined by the sponsor and investigators after data review.

Part B dose expansion cohort B will occur once dose escalation has achieved a dose that has both acceptable safety and achieves drug exposures predicted to have activity in R/R B-cell lymphomas. See Appendix D for the background, rationale, and determinants of the decision to open dose expansion cohort B.

- Expansion Cohort A: 20 participants with advanced solid malignancies showing preclinical sensitivity or molecular markers of sensitivity to PCLX-001: breast, non-small cell lung, small-cell lung, colorectal, and bladder cancers
- Expansion Cohort B: 20 participants with relapsed/refractory (R/R) B-cell lymphoma: diffuse large B-cell lymphoma (including transformed disease), high grade B-cell lymphoma, follicular lymphoma, mantle cell lymphoma, and Burkitt lymphoma.

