4.1 Inclusion Criteria

Patient must meet all of the following criteria to be eligible for the study.

The following inclusion criteria apply to ALL (dose-escalation and expansion) patients:

1. Ability to understand and the willingness to sign a written informed consent. A signed informed consent must be obtained before any study-specific procedures are performed.
2. Male or female patients aged \geq 18 years
3. **Dose Escalation**
 - a. Participants with histologically-confirmed advanced solid tumor (non-breast cancer) who have failed at least one prior therapy and/or are not eligible for therapies expected to provide clinical benefit.
 - b. Participants with histologically-confirmed metastatic breast cancer with known hormone receptor status meeting the therapy requirements as listed below (just prior to criterion #4).
 - c. Histologically-confirmed B-cell lymphomas that are expected to express CD20 including DLBCL, HGBL, FL (grades 1 to 3b), MCL, and Burkitt lymphoma who have failed at least two prior therapies and/or are not eligible for therapies expected to provide clinical benefit (including autologous stem cell transplantation). Transformed large B-cell lymphoma patients are eligible. FL patients should meet criteria for requiring treatment. These histologic subtypes are based on WHO 2016 criteria.

Dose Expansion

Cohort A: Participants with histologically-confirmed advanced NSCLC, SCLC, colorectal, and bladder cancers who have failed at least one prior therapy and/or are not eligible for therapies expected to provide clinical benefit. Participants with histologically-confirmed metastatic breast cancer with known hormone receptor status meeting the therapy requirements as listed below (just prior to criterion #4).

Cohort B: Participants with histologically-confirmed R/R B-cell lymphomas that are expected to express CD20 including DLBCL, HGBL, FL (grades 1-3a), FL (grade 3b), MCL, and

Burkitt lymphoma who have failed at least two prior therapies and/or are not eligible for therapies expected to provide clinical benefit. Transformed large B-cell lymphoma patients are eligible. FL patients should meet criteria for requiring treatment.

Therapy requirements and stratification factors for histologically-confirmed metastatic breast cancer participants in either the dose escalation or dose expansion phases are dependent upon hormone receptor status as follows:

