i. **Estrogen Receptor positive and/ or Progesterone Receptor positive, and HER 2 negative disease.**

Prior treatment with:

- Two or more lines of endocrine therapy in the adjuvant or metastatic setting including the following: Selective Estrogen Receptor Modulators (eg. tamoxifen), Aromatase Inhibitors (eg. letrozole, anastrozole, exemestane), Selective Estrogen Receptor Downregulators (fulvestrant), and CDK4/6 inhibitors (palbociclib, ribociclib, abemaciclib) in combination or monotherapy, and
- at least three lines of cytotoxic chemotherapy given in the adjuvant, neoadjuvant, or metastatic setting including an anthracycline, a taxane, and capecitabine.

ii. **Estrogen Receptor and Progesterone Receptor and HER2 negative disease.**

- Prior treatment with at least three lines of cytotoxic chemotherapy in the adjuvant or metastatic setting including the following agents: anthracyclines, taxanes, platinum (carboplatin or cisplatin), and
- if known BRCA1 or BRCA2 mutated disease, prior PARP inhibitor therapy is required if available to the patient.

iii. **HER2 positive disease with negative Estrogen receptors.**

- Prior treatment with three or more lines of HER2-directed therapy in the adjuvant, neoadjuvant, or metastatic setting including at least three of the following HER2 directed agents: trastuzumab, trastuzumab emtansine, trastuzumab deruxtecan, pertuzumab, lapatinib, neratinib, tucatinib.

iv. **HER2 positive disease with positive Estrogen receptors.**

Prior treatment with:

- three or more lines of HER2-directed therapy in the adjuvant, neoadjuvant, or metastatic setting including at least three of the following HER2 directed agents: trastuzumab, trastuzumab emtansine, trastuzumab deruxtecan, pertuzumab, lapatinib, neratinib, tucatinib, and
- two or more lines of endocrine therapy in the adjuvant or metastatic setting including the following: Selective Estrogen Receptor Modulators (eg. tamoxifen), Aromatase Inhibitors (eg. letrozole, anastrozole, exemestane), Selective Estrogen Receptor Downregulators (fulvestrant), and CDK4/6 inhibitors (palbociclib, ribociclib, abemaciclib) in combination or monotherapy, and
- at least three lines of cytotoxic chemotherapy given in the adjuvant, neoadjuvant, or metastatic setting including an anthracycline, a taxane, and capecitabine.

4. Patients must have evaluable or measurable disease (as per Response Evaluation Criteria in Solid Tumors, version 1.1 [RECIST 1.1], or the Lugano lymphoma classification).

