4.3 Replacement

Patients who discontinue due to a DLT in Cycle 1 will not be replaced.

Patients who discontinue during Cycle 1 due to any reason other than a DLT and patients who were non-compliant in Cycle 1 will be replaced for the purpose of Cycle 1 DLT determinations, but may continue on the study at the discretion of the investigator. Non-compliance is determined by the investigator and can include failure to take medications or failure to have study-related activities performed.

Patients who took less than 21-days of the required dose of study drug during Cycle 1 will be replaced for the purpose of Cycle 1 DLT determinations, but may continue on the study at the discretion of the investigator.

Patients with insufficient PK data may have to be replaced. The decision to replace a patient due to insufficient PK data will be taken on a case-by-case basis after consultation between the investigator and the sponsor.

Patients who discontinue after Cycle 1 will not be replaced.

If the dropout rate in any expansion cohort is $\geq 20\%$, additional patients may be enrolled to ensure that at least 20 patients per indication will be evaluable for the response assessment.

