8. STATISTICAL CONSIDERATIONS

8.1 Sample Size Determination

The exact sample size for Part A dose-escalation cannot be pre-determined and depends on the number of cohorts needed to reach MTD. Part A will enroll at least 9 patients and up to 52 patients. In Part B, there are two expansion cohorts of 20 patients each for a total of 40 patients.

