- Measurements are not required but these lesions should be noted at baseline and should be followed as “present,” “absent,” or “unequivocal progression.”

Determining Response

- Assess at baseline and on study with consistent modalities (CT, MRI, PET/CT).
 - Measure target lesions and calculate SLD.
 - Visually assess nontarget lesions.
 - Search for new lesions.
 - Combine these assessments into the overall response.

Target Lesion Response

Complete response (CR)	
• Disappearance of all extranodal target lesions.• All pathological lymph nodes must have decreased to <10 mm in short axis.
Partial response (PR)	
• At least a 30% decrease in the SLD of target lesions, taking as reference the baseline sum diameters.
Progressive disease (PD)	
• SLD increased by at least 20% from the smallest value on study (including baseline, if that is the smallest).• SLD must also demonstrate an absolute increase of at least 5 mm. (2 lesions increasing from, for example, 2 mm to 3 mm, does not qualify).
Stable disease (SD)	
• Neither sufficient shrinkage to qualify for PR nor sufficient increase to qualify for PD.
Nonevaluable (NE)	
• One or more lesions cannot be evaluated because of missing data or poor image quality unless a convincing argument can be made that the contribution of the individual missing lesion(s) would not change the assigned time point response (eg, PD based on other findings).

Abbreviations: SLD, sum of the longest diameters.

Nontarget Lesion Response

Complete response (CR)	
• Disappearance of all extranodal nontarget lesions.• All lymph nodes must be nonpathological in size (<10 mm short axis).• Normalization of tumor marker level.
Non-CR/non-PD	
• Persistence of 1 or more nontarget lesions(s) and/or maintenance of tumor marker level above the normal limits.
Progressive disease (PD)	
• Unequivocal progression of existing nontarget lesions (subjective judgment by experienced reader).

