Unable to evaluate (UE)	
• One or more lesions cannot be evaluated because of missing data or poor image quality unless a convincing argument can be made that the contribution of the individual missing lesion(s) would not change the assigned time point response (eg, PD based on other findings).

New Lesions

- Should be unequivocal and not attributable to differences in scanning technique or findings which may not be a tumor (does not have to meet criteria to be "measurable").
- If a new lesion is equivocal, continue to next time point. If confirmed then, PD is assessed at the date when the lesion was first seen.
- Lesions identified in anatomic locations not scanned at baseline are considered new.
- New lesions on ultrasound should be confirmed on CT or MRI.

Evaluation of Overall Time Point Response for Patients With Measurable Disease at Baseline

Abbreviations: CR, complete response; PR, partial response; PD, progressive disease; SD, stable

Target Lesions	Nontarget Lesions	New Lesions	Overall Response
CR	CR	No	CR
CR	Non-CR/non-PD	No	PR
CR	NE	No	PR
PR	Non-PD or NE	No	PR
SD	Non-PD or NE	No	SD
Not all evaluated	Non-PD	No	NE
PD	Any	Yes or no	PD
Any	PD	Yes or no	PD
Any	Any	Yes	PD

disease; NE, nonevaluable.

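### Part B admits patients without measurable disease, who in Cohort A can reach CR but not PR yet stay in the efficacy population; define a response-evaluable denominator

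*Combined protocol and SAP*

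**What the plan says.** Section 4.1 opens with "The following inclusion criteria apply to ALL (dose-escalation and expansion) patients". Criterion 4 then reads "Patients must have evaluable or measurable disease", by RECIST 1.1 or Lugano. It is not split by part, although criteria 3 and 7c are.

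The purpose of Part B is given in Section 3.5: "Two expansion cohorts will be opened to determine the preliminary clinical activity of PCLX-001". Section 8.1 sets its size: "In Part B, there are two expansion cohorts of 20 patients each for a total of 40 patients". Section 3.5 also names the overall response rate (ORR) among the inputs to the RP2D.

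For solid tumours, Appendix B defines PR as "At least a 30% decrease in the SLD of target lesions, taking as reference the baseline sum diameters". Target lesions are picked from measurable ones. Non-target disease can be CR, non-CR/non-PD, PD or unable to evaluate, with no PR category. The one overall-response table in Appendix B is headed "Evaluation of Overall Time Point Response for Patients With Measurable Disease at Baseline".

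For lymphoma, Appendix C gives two routes to partial response. The CT route needs a fall in the summed products of measurable sites. The PET-CT route needs reduced uptake and accepts a residual mass of any size. Section 7.3 makes PET-CT optional.

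Table 8-1 places in the efficacy population anyone who was dosed and then had a tumour assessment on treatment. Section 4.3 adds that, if dropout in an expansion cohort reaches 20%, "additional patients may be enrolled to ensure that at least 20 patients per indication will be evaluable for the response assessment". It does not say what makes a patient evaluable in that sense.

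**The concern.** The entry rule and the response instrument do not match in Part B. Because criterion 4 offers evaluable disease as an alternative to measurable disease, it must admit some patients with no measurable lesion. Appendix B lists pleural effusion, ascites, inflammatory breast disease and lymphangitic spread in skin or lung as truly non-measurable. Breast and lung cancers are Cohort A tumour types, so such entrants are foreseeable.

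These patients have one route to response (CR) where others have two, but they count fully in the efficacy population. In a cohort of 20 each patient is worth 5 percentage points. The reported rate would then depend partly on how many such patients the sites happen to enrol, and a reader could not separate that from the activity of the drug.

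**Working it through.** **The plan's own figure.** 2 × 20 = 40 agrees with Section 8.1. The 20 per cohort cannot be re-derived, because no null or target rate, alpha, power or interval width is stated.

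**Who can reach what, if no lesion is measurable at baseline**

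| Setting | CR | PR |
|---|---|---|
| Cohort A, RECIST (Appendix B) | Possible, through non-target CR | Not possible: no target lesions, so no baseline sum |
| Cohort B, CT only (Appendix C) | Possible | Not possible: needs measurable sites |
| Cohort B, PET-CT, FDG-avid (Appendix C) | Possible | Possible: based on uptake |

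**Does another section correct this?** Section 7.3 describes objective response in solid tumours for measurable lesions only, and gives no rule for other patients. The Section 4.3 top-up starts only at 20% dropout; a patient without measurable disease who stays on study is not a dropout. Section 8.4 plans descriptive statistics for population and toxicity, and states no ORR denominator.

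**Size.** Let k be the number of the 20 who have no route to PR, p the response rate in measurable disease and c the CR rate in those k patients. All three are assumptions.

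Expected ORR = [p(20 − k) + c·k] / 20

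Difference from p = k(c − p) / 20, which is negative exactly when c < p.

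With p = 20%:

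| k | c = 0 | c = 5% | c = 10% |
|---|---|---|---|
| 2 | 3.6/20 = 18% | 3.7/20 = 18.5% | 3.8/20 = 19% |
| 4 | 3.2/20 = 16% | 3.4/20 = 17% | 3.6/20 = 18% |
| 6 | 2.8/20 = 14% | 3.1/20 = 15.5% | 3.4/20 = 17% |

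With c = 0 and k = 2, 4 or 6, other values of p give:
- p = 10%: 9%, 8%, 7%
- p = 30%: 27%, 24%, 21%
- p = 40%: 36%, 32%, 28%

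For p = 20% and c = 0, the binomial chance of at least 3 responses falls from 0.794 (k = 0) to 0.729, 0.648 and 0.552.

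**Precision with a restricted denominator** (exact 95% intervals, 4 responders, all in measurable disease):
- 4/20 = 20.0% (5.7–43.7)
- 4/18 = 22.2% (6.4–47.6)
- 4/16 = 25.0% (7.3–52.4)
- 4/14 = 28.6% (8.4–58.1)

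With no responders, the upper limit is 16.8% on 20 patients, 20.6% on 16 and 23.2% on 14. Counting patients who have no route to PR therefore makes a negative result look firmer than it is.

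**The case against.** Several objections stand, and they set the limits of the point.

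- **Cohort B.** A reader might infer that nobody without measurable disease can reach a partial response anywhere in Part B. Appendix C does not support that: an FDG-avid patient followed by PET-CT can. Appendix B does not apply to that cohort at all.
- **CR.** A reader might treat these patients as certain non-responders. Appendix B allows CR on non-target disease, so c = 0 is the extreme case, not the expected one.
- **The missing table.** Appendix B declares itself a summary and sends the reader to its source. The absence of an overall-response table for non-target-only disease is therefore weak evidence of a gap. The PR definition and Table 8-1 carry the argument without it.
- **RP2D.** A reader might infer that a diluted ORR would distort dose selection. Section 3.5 opens Cohort A only after the MTD and RP2D are determined, while also saying that the RP2D draws on data from all parts. For Cohort A the link is at best ambiguous, and this point does not rest on it.
- **Stakes.** Anti-tumour activity is a secondary objective with no hypothesis or threshold. At p = 20% and c = 0 the expected loss is 0.4, 0.8 or 1.2 responders in 20, small against an interval of 5.7–43.7% for 4/20.

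On the other side, Table 8-1 defines a general efficacy population and does not expressly call it the ORR denominator. It is, however, the only efficacy population in the plan, so an analyst following the plan would use it.

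**Conclusion.** The mismatch is real for Cohort A and for those Cohort B patients who are assessed by CT alone. Following the stated rules biases the Part B response rate downward whenever CR in patients without measurable disease is rarer than response in measurable disease. Under the illustrative assumptions (p = 20%, c between 0 and 10%, 2 to 6 such patients in 20) the shift is 1 to 6 percentage points. The share of such patients is assumed throughout, and if none enrol there is no bias.

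No stated error rate, power or decision threshold is broken. The result is bias and ambiguity in a descriptive secondary estimate. This is a cheap improvement, not a flaw that threatens the trial.

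**What to change.** Add to Table 8-1 a Part B response-evaluable set and name it as the ORR denominator:

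- Cohort A: measurable disease at baseline by RECIST 1.1.
- Cohort B: CT-measurable disease at baseline, or, where PET-CT is used, FDG-avid disease on a baseline PET-CT with follow-up by PET-CT.

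For the PET-CT group, say that a patient who progresses before the follow-up PET-CT stays in the set as a non-responder. Otherwise early progressors would leave the denominator and the bias would turn upward.

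List the remaining patients separately by best category (CR, non-CR/non-PD, PD, NE in Cohort A; the matching Lugano categories in Cohort B). Use the same definition for response-evaluable patients in Section 4.3.

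Optionally, require measurable disease at entry for Cohort A only, in the synopsis and Section 4.1. A blanket rule requiring a measurable lesion in Cohort B would go too far, because it would exclude FDG-avid patients whose response Appendix C can assess. Part A, which is driven by DLT, can keep the wider criterion.

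Cost: a few lines of text, and a somewhat smaller denominator with a wider interval, as shown above. If the sponsor wants 20 patients with measurable disease in a cohort without restricting entry, assumed non-measurable shares of 10%, 20% or 30% imply enrolling 23 (20/0.9), 25 (20/0.8) or 29 (20/0.7). Restricting entry to Cohort A would slow its accrual slightly.

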4.2 Exclusion Criteria

The following exclusion criteria apply to ALL (Dose-escalation and expansion) patients:

1. Known hypersensitivity to the study drugs or excipients of the preparations or any agent given in association with this study
2. History of cardiac disease: congestive heart failure New York Heart Association (NYHA) class > II, unstable angina (angina symptoms at rest), new-onset angina (within the past 6 months before study entry), myocardial infarction within the past 6 months before study enrollment date, or uncontrolled cardiac arrhythmias
3. Uncontrolled arterial hypertension despite optimal medical management (per investigator's opinion)
4. Moderate or severe hepatic impairment, i.e. Child-Pugh class B or C
5. Patients with known human immunodeficiency virus (HIV) infection
6. Patients who have an active hepatitis B virus (HBV) or hepatitis C virus (HCV) infection requiring treatment. Patients with chronic HBV or HCV infection are eligible at the investigator's discretion provided that the disease is stable and sufficiently controlled under treatment.
7. Patients with significantly impaired liver function as assessed by the following laboratory tests to be conducted within 7 (± 3) days before the first dose of study drug:
 - Total bilirubin \geq 1.5 times the upper limit of normal (ULN), and/or
 - Alanine aminotransferase (ALT) and aspartate aminotransferase (AST) \geq 3 times ULN or \geq 5 times ULN for patients with malignant liver involvement.
8. Infections of CTCAE Grade 2 not responding to therapy or active clinically serious infections of CTCAE Grade > 2
9. Symptomatic metastatic brain or meningeal tumors unless the patient is $>$ 3 months from definitive therapy, has a stable imaging study within 4 weeks prior to the first dose of study drug and is clinically stable with respect to the tumor at the time of study entry. Patients with asymptomatic brain metastases must not be on steroid therapy. Patients with neurological symptoms should undergo a CT / MRI scan of the brain to exclude new or progressive brain metastases.
10. Current or past history of central nervous system (CNS) lymphoma

11. Uncontrolled seizure disorder requiring therapy (e.g. strong CYP3A4 inducers such as carbamazepine and phenytoin)
12. History of organ allograft transplantation or autologous stem cell transplantation \leq 3 months prior to the first dose of study drug. Patients who received prior CAR-T or other T-cell targeting treatment (approved or investigational) \leq 4 weeks prior to study drug administration
13. Evidence or history of bleeding disorder, i.e. any hemorrhage / bleeding event of CTCAE Grade $>$ 2 within 4 weeks before the first dose of study drug
14. Serious, non-healing wound, ulcer, or bone fracture
15. Previous or concurrent cancer that is distinct in primary site or histology from the cancer being evaluated in this study, with the exception of the following previous or concurrent cancer types:
 - Curative treatment for localized cancer completed without signs of recurrence and treatment-related toxicity and low risk of recurrence as assessed by the investigator,
 - *In-situ* prostate cancer, Gleason Score $<$ 7, prostate-specific antigen $<$ 10 ng/mL (very low risk and low risk, according to therapy guidelines, e.g. the National Comprehensive Cancer Network guideline; active surveillance / observation is a recommended option).
16. Any clinical condition that is considered unstable or might jeopardize the safety of the patient and his / her compliance in the study
17. Inability to swallow oral medications
18. Any malabsorption condition
19. Breastfeeding. Female patients must not breastfeed during treatment and until 4 months after last study drug administration.
20. Treatment with anticancer chemotherapy or immunotherapy during the study or within 3 weeks before the first dose of study drug. For small-molecule drugs, a period of at least 3 half-lives before the first dose of study drug is acceptable. Mitomycin C or nitrosoureas should not be given within 6 weeks before the first dose of study drug.
21. Treatment with systemic steroids (prednisone dose \geq 10 mg/day or equivalent dose).
22. Acute toxic effects (CTCAE Grade \geq 2) of previous anticancer chemotherapy or immunotherapy that have not yet stabilized or if significant post-treatment toxicities have been observed. (Note however that toxic effects of previous anticancer therapy considered as chronic, such as chemotherapy-induced neuropathy, fatigue, alopecia, or anorexia of CTCAE Grade $<$ 2, for which further resolution is not expected, do not prevent participation in this study.)
23. Radiotherapy to target lesions in the 21 days before starting the first dose of study drug. Palliative radiotherapy is allowed to non-target lesions at any time before starting the first dose of study drug.
24. Major surgery or significant trauma within 4 weeks before the first dose of study drug
25. Previous assignment to treatment during this study
26. Concomitant participation in another clinical study with investigational medicinal product(s)
27. Substance abuse, medical, psychological, or social conditions that may interfere with the patient's participation in the study or evaluation of the study results
28. Close affiliation with the investigational site; e.g. a close relative of the investigator, dependent person (e.g. employee or student of the investigational site)
29. Use of strong CYP3A4 inhibitors and inducers from 14 days prior to first administration of study drug. Strong CYP3A4 inhibitors and inducers are prohibited during the study and until the active FU visit.
30. Use of Proton Pump Inhibitors (PPIs) must be discontinued at least 48 hours prior to initiation of study drug.

Note: If a potential participant is on a PPI and requires some form of Acid Reducing Agent(s) (ARAs), the investigator should consider alternatives for the duration of the trial, including Famotidine, or oral antacid drugs such as calcium carbonate.

31. Clinically relevant findings in the ECG such as a second- or third-degree atrioventricular block, prolongation of the QRS complex > 120 ms (except for bundle branch block pattern), or prolongation of the QTc interval (Fridericia) over 450 ms unless agreed otherwise between the investigator and the sponsor's medically responsible person.

